### 5.1.1 Significance Levels and Adjustment for Multiple Endpoints

The trial will be viewed as positive as regards to efficacy if statistical significance is obtained in the primary analysis for either primary endpoint. To adjust for multiple endpoints the Hochberg procedure will be used. As the two primary endpoints evaluate the same outcome, in all study subjects for the first primary endpoint and in subjects with mild disease for the second primary endpoint, then they are highly correlated. If for example in the primary analyses of the two primary endpoints there are 98 mild subjects and 76 moderate subjects then the correlation is  $[98/174]^{0.5}$ , and then as shown by Spiessens & Debois (2010) a higher significance level can be used while still maintaining the maximum experimentwise type 1 error at the target  $\alpha$ .

The Hochberg procedure (allowing for this correlation) proceeds as follows when the overall  $\alpha$  =0.025 one-sided: (i) If both (one-sided) p-values for the two primary endpoints are  $< 0.025$  then both primary endpoints are declared statistically significant; or (ii) If the largest (one-sided) p-value is  $\geq 0.025$  and the smallest (one-sided) p-value  $< 0.0144$  then statistical significance can be declared for this one primary endpoint.

Testing for the primary endpoints is also carried out using an overall  $\alpha$  =0.050 one-sided. In this case the Hochberg procedure (allowing for this correlation) proceeds as follows: (iii) If both

(one-sided) p-values for the two primary endpoints are  $< 0.050$  then both primary endpoints are declared statistically significant; or (iv) If the largest (one-sided) p-value is  $\geq 0.050$  and the smallest p-value  $< 0.0297$  then statistical significance can be declared for this one primary endpoint.

Note: The value of 0.0144 has been determined numerically (using the SAS PROBBNRM function) under the Hochberg procedure to control the maximum experimentwise type 1 error at 0.025 one-sided. Similarly, the value of 0.0297 has been determined numerically under the Hochberg procedure to control the maximum experimentwise type 1 error at 0.050 one-sided. Each value has been derived based on the assumption of 98 subjects with mild disease at baseline, and 76 with moderate disease at baseline in the FAS population for the Final Cohort. However, these  $\alpha$  values will be recalculated if the final counts differ from these values.

P-values for the one or both primary endpoints where for their primary analysis have statistical significance from (i) or (ii) under the Hochberg procedure (where the overall  $\alpha = 0.025$  one-sided) will be flagged with "\*\*\*". If p-values for the primary analysis of one or both primary endpoints are only statistically under (iii) or (iv) of the Hochberg procedure (where the overall  $\alpha = 0.050$  one-sided) then they will be flagged with \*\*".

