### 3.3 Sample Size Determination

The target number of subjects to be randomized per cohort is 30 individuals seronegative for SARS-CoV-2 Spike IgG antibodies (20 subjects to the RD-X19 treatment arm and 10 subjects for Sham control), for a minimum total of 60 subjects. At the sponsors option, the total number of subjects can be increased by an additional 150 total subjects to include all serostatuses after a dose has been selected based on adequate safety/tolerability observed for the final dose cohort.

Based on findings in the EB-P12-01, the hazard ratio observed for the time to sustained symptom resolution in that early feasibility trial was HR=0.4 between active RD-X19 and Sham.

The increased sample size in the Final Cohort (up to 180 total), with an anticipated roughly equal number of antibody positive to negative individuals enrolled during the option, will lead to approximately 90 seropositive and 90 seronegative subjects. The modified Full Analysis Set (mFAS) population containing only antibody negative subjects (as defined in Section 4, 60 RD-X19: 30 Sham) has at least 90% power to detect meaningful changes in SARS-CoV-2 symptom resolution from baseline (Hazard ratio of 0.4) for the first primary endpoint. These power calculations assume that testing will be carried out using  $\alpha = 0.025$  one-sided, up to a 20% dropout rate due to discontinuations or hospitalizations, as well as an assumption that the proportions of subjects having the event (for the first primary endpoint) by Day 14 is 85% for the RD-X19 arm and 75% for the Sham arm.

In the Full Analysis Set (FAS) for the Final Cohort, the primary analysis population including all randomized subjects receiving at least one treatment, the increased sample size (increase by a minimum of 100 RD-X19: 50 Sham) has at least 90% power to detect a Hazard ratio of 0.5 between RD-X19 and Sham for the first primary endpoint. These power calculations assume that testing will be carried out using  $\alpha = 0.025$  one-sided, as well as an assumption that the proportions of subjects having the event (for the first primary endpoint) by Day 14 is 90% for the RD-X19 arm and 85% for the Sham arm, with adjustment for multiple endpoints as described in Section 5.1.1.

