Note: The two primary endpoints will be tested using a maximum experimentwise type 1 error of 0.025 1-sided and using a maximum experimentwise type 1 error of 0.050 1-sided. In section 5.1.1, under the procedure for multiple endpoint adjustment, the significance levels for testing each of the two individual primary endpoints are derived so that the maximum experimentwise type 1 error is 0.025 one-sided, and significance levels are also derived so that the maximum experimentwise type 1 error is 0.050 one-sided.

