  - Who have RR  $\geq 20$  at Baseline
  - Who report Shortness of Breath at Baseline, or
  - Who have clinical signs suggestive of lower airway involvement.
- 3) gender
- 4) age (grouping of <50,  $\geq 50$ )
- 5) baseline antibody status (positive, negative)

Note: For the second primary efficacy endpoint the term for baseline disease status of mild vs. moderate will not be included.

Two-sided 95% confidence intervals and two-sided 90% confidence intervals will also be derived for the hazard ratios from the above models.

Supportive analyses in each case for the two primary efficacy endpoints will be produced for the mFAS and the Per Protocol population. For the mFAS population the Cox proportional hazards regression model will not include the covariate related to baseline antibody status.

All of the above analyses of the primary endpoints will also be produced for pooled RD-X19 doses vs. pooled Sham, and for RD-X19 low dose (i.e., the dose not expanded to produce the Final Cohort) vs. Pooled Sham, but where in all cases these p-values will be viewed as descriptive only. For the analyses of pooled RD-X19 vs. pooled Sham the log-rank test and the Cox proportional hazards models will each be stratified by cohort.

Following notations are used in the sample SAS code:

- TRT: treatment group with values 1 for RD-X19 from Final Cohort, 2 for RD-X19 from Cohort A, and 3 for Sham from Final Cohort, 4 for Sham from Cohort A
- TRTpooL: value 12 for pooled RD-X19 from both cohorts, 3 for pooled Sham
- COHORT: A for first cohort, B for Final cohort
- HOURS: time to sustained resolution of COVID-19 signs and symptoms
- CNSR: the censoring variables, 1 for censored, 0 for not censored
- COVIDSEV: grouping of COVID-19 Composite Severity Score at baseline, 1 for score <1.25, 2 for score  $\geq 1.25$
- DSSTATUS: baseline disease status, 1 for mild, 2 for moderate
- SEX: 1 for males, 2 for females
- AGEGRP: grouping of age, 1 for age <50, 2 for age  $\geq 50$
- ANTIBODY: grouping of baseline antibody status, 1 for positive, 2 for negative

Sample SAS Code for Main Analysis

1. Unstratified analysis of Primary Endpoint 1: Time to sustained resolution of COVID-19 signs and symptoms (in mild and moderate subjects)

a) RD-X19 from Final Cohort vs Sham from Final Cohort, log-rank test (unstratified)

```
PROC LIFETEST DATA=datain CONFTYPE=LINEAR;  
  WHERE trt in (1,3);  
  TIME hours*cnsr(1);  
  STRATA trt/ TEST=LOGRANK;  
RUN;
```

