Geometric Mean on Original Scale[2]	XX.X	XX.X	XX.X	XX.X	XX.X

Source: Listing 16.x.x

[1] COVID-19 Composite Severity Score (CSS) is defined as the sum of the eight individual COVID-19 signs and symptoms severity scores divided by eight. Subjects with scores missing for one or more symptoms will have CSS calculated as the sum of all scores reported divided by the number of scores reported.

[2] Geometric Means are computed by exponentiating (base 10) the Means of the log10-transformed viral load.

O:\Studies\EmitBio\EB-P20-01\Biometrics\Programs\Tables\xxx.sas ran on Month Day, Year at hh:mm on data from Month Day, Year.

Table 14.2.1.1 – Primary Analysis and Supportive Analyses of the First Primary Efficacy Endpoint: Time (Hours) to Sustained Resolution of COVID-19 Signs and Symptoms for the Final Cohort

Population	Statistics	Final Cohort RD-X19	Final Cohort Sham
Full Analysis Set (FAS) #			
N		XX	XX
n (%) Censored		XX (XX.X)	XX (XX.X)
Median of Time to Sustained Resolution (95% CI)		XX.X (XX.X, XX.X)	XX.X (XX.X, XX.X)
25 th Percentile of Time to Sustained Resolution (95% CI)		XX.X (XX.X, XX.X)	XX.X (XX.X, XX.X)
75 th Percentile of Time to Sustained Resolution (95% CI)		XX.X (XX.X, XX.X)	XX.X (XX.X, XX.X)
1-sided P-value for treatment comparison from Log-rank Test 		0.XXXX	
2-sided P-value for treatment comparison from Log-rank Test 		0.XXX	
Final Cohort RD-X19 to Final Cohort Sham Hazard Ratio 		X.XXX	
95% CI 		(X.XXX, X.XXX)	
90% CI 		(X.XXX, X.XXX)	
P-value for treatment comparison from Cox PH Regression 		0.XXX	
Final Cohort RD-X19 to Final Cohort Sham Hazard Ratio adjusted for Covariates		0.XXX	
95% CI 		(X.XXX, X.XXX)	
90% CI 		(X.XXX, X.XXX)	
P-value for treatment comparison from Cox PH Regression 		0.XXX	
Modified Full Analysis Set (mFAS)			
N		XX	XX
n (%) Censored		XX (XX.X)	XX (XX.X)
Median of Time to Sustained Resolution (95% CI)		XX.X (XX.X, XX.X)	XX.X (XX.X, XX.X)
25 th Percentile of Time to Sustained Resolution (95% CI)		XX.X (XX.X, XX.X)	XX.X (XX.X, XX.X)
75 th Percentile of Time to Sustained Resolution (95% CI)		XX.X (XX.X, XX.X)	XX.X (XX.X, XX.X)
P-value for treatment comparison from Log-rank Test 		0.XXX	
Final Cohort RD-X19 to Final Cohort Sham Hazard Ratio 		X.XXX	
95% CI 		(X.XXX, X.XXX)	

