90% CI 		(X.XXX, X.XXX)	
P-value for treatment comparison from Cox PH Regression 		0.XXX	
Final Cohort RD-X19 to Final Cohort Sham Hazard Ratio adjusted for Covariates 		0.XXX	
95% CI 		(X.XXX, X.XXX)	

90% CI 	(X.XXX, X.XXX)
P-value for treatment comparison from Cox PH Regression 	0.XXX
Per Protocol (PP) Population	
N	XX
n (%) Censored	XX (XX.X)
Median of Time to Sustained Resolution (95% CI)	XX.X (XX.X, XX.X)
25 th Percentile of Time to Sustained Resolution (95% CI)	XX.X (XX.X, XX.X)
75 th Percentile of Time to Sustained Resolution (95% CI)	XX.X (XX.X, XX.X)
P-value for treatment comparison from Log-rank Test 	0.XXX
Final Cohort RD-X19 to Final Cohort Sham Hazard Ratio 	X.XXX
95% CI 	(X.XXX, X.XXX)
90% CI 	(X.XXX, X.XXX)
P-value for treatment comparison from Cox PH Regression 	0.XXX
Final Cohort RD-X19 to Final Cohort Sham Hazard Ratio adjusted for	
Covariates 	0.XXX (0.XXX, 0.XXX)
95% CI 	(X.XXX, X.XXX)
90% CI 	(X.XXX, X.XXX)
P-value for treatment comparison from Cox PH Regression 	0.XXX

Abbreviation: CI = Confidence Interval, PH = Proportional Hazards

#The primary analysis of the endpoint is the log-rank test performed for the Full Analysis Set. For the p-values for the primary analysis, \*\* denotes statistically significant using the procedure for multiple endpoint adjustment with an overall  $\alpha = 0.025$  one-sided; \* denotes statistically significant using the procedure for multiple endpoint adjustment with an overall  $\alpha = 0.050$  one-sided.

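### SAP 5.1.1 does not say which of its two Hochberg levels makes the trial positive; read literally, the success rule has 5.0% one-sided error, against the 2.5% used for power

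*SAP*

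**What the plan says.** The protocol gives no significance level. Section 10.1 limits hypothesis testing to the two primary endpoints (sustained symptom resolution in all subjects, and in subjects with mild disease at baseline), and section 10.4.1 leaves the multiplicity adjustment to the SAP.

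SAP 5.1.1 opens with the success rule: "The trial will be viewed as positive as regards to efficacy if statistical significance is obtained in the primary analysis for either primary endpoint". It then gives two procedures:

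- **Overall one-sided 0.025.** Rule (i): both endpoints are significant if both p-values are below 0.025. Rule (ii): otherwise the smaller p-value must be below 0.0144.
- **Overall one-sided 0.050.** Introduced by "Testing for the primary endpoints is also carried out using an overall" level of 0.050. Rules (iii) and (iv) have the same form, with 0.050 and 0.0297.

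The Note in SAP 3.3 says the endpoints will be tested "using a maximum experimentwise type 1 error of 0.025 1-sided and using a maximum experimentwise type 1 error of 0.050 1-sided", and ranks neither. The flagging text in 5.1.1 gives a lesser mark to p-values that "are only statistically under (iii) or (iv) of the Hochberg procedure". The footnotes to Tables 14.2.1.1 and 14.2.1.2 use the same phrase for both marks: each "denotes statistically significant using the procedure for multiple endpoint adjustment with an overall" alpha, 0.025 for one mark and 0.050 for the other.

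In SAP 3.3, both power statements assume one-sided 0.025. The one for the full analysis set (FAS) adds "with adjustment for multiple endpoints as described in Section 5.1.1".

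**The concern.** The success sentence depends on a term, statistical significance, that the SAP then defines at two levels. Nothing says that only the stricter one counts. A result that meets rule (iii) or (iv) but neither (i) nor (ii) is statistically significant by the SAP's own table footnote, and so satisfies the success sentence.

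The SAP does demote p-values elsewhere. For the pooled-dose and low-dose analyses of the same endpoints, SAP 5.5.1 adds "but where in all cases these p-values will be viewed as descriptive only". Rules (iii) and (iv) carry no such label and are presented as tests of the primary endpoints.

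The borderline result is where a prespecified rule is needed. As the text stands, whether that result is a positive trial could be settled after unblinding. The error rate of the literal rule is also twice the one on which the power statements rest.

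**Working it through.** **Inputs.** From SAP 5.1.1: 98 mild and 76 moderate subjects (174 in all), correlation √(98/174) = 0.7505, thresholds 0.0144 and 0.0297. From SAP 3.3: design hazard ratio 0.5 for the FAS, 100:50 as the minimum expansion, up to 180 in the Final Cohort, event proportions 90% (RD-X19) and 85% (sham), 2:1 allocation.

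**1. Reproducing the SAP's thresholds.** Let B(a,b) be the null probability that one p-value is below a and the other below b, from the bivariate normal with correlation 0.7505. A procedure with overall level α and single-endpoint threshold c has

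error = [2c − B(c,c)] + [B(α,α) − 2B(c,α) + B(c,c)].

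Setting the error equal to α and solving gives c = 0.01444 for α = 0.025 and c = 0.02970 for α = 0.050. Both SAP values are reproduced.

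**2. Error of each procedure at the printed thresholds.**

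- Rules (i)–(ii): B(c,c) = 0.00491, B(α,α) = 0.00953, B(c,α) = 0.00670. Error = 0.02389 + 0.00105 = 0.0249.
- Rules (iii)–(iv): B(c,c) = 0.01174, B(α,α) = 0.02203, B(c,α) = 0.01572. Error = 0.04766 + 0.00233 = 0.0500.

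**3. Error of the literal success rule.** Since 0.025 < 0.050 and 0.0144 < 0.0297, every result that passes (i)–(ii) also passes (iii)–(iv). Significance under either procedure is therefore the same event as passing (iii)–(iv), with error 0.0500. A simulation of 20 million null trials gave 0.0249, 0.0500 and 0.0500 for the first procedure, the second and their union, and none passed the first but failed the second. The share of null trials that pass only the second is 0.0500 − 0.0249 = 0.0251.

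**4. What tying success to 0.025 costs at hazard ratio 0.5.** Events are:

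- 150 subjects: 100×0.90 + 50×0.85 = 132.5
- 174 subjects: 116×0.90 + 58×0.85 = 153.7
- 180 subjects: 120×0.90 + 60×0.85 = 159

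The mean of the first log-rank statistic is |ln 0.5|·√(events × 2/9). The mean of the second is that value times 0.7505, assuming the same hazard ratio in mild and moderate subjects. The chance of success on either endpoint is then:

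| Events | Means of Z1, Z2 | (i)–(ii) decide | (iii)–(iv) decide | Pass second only |
|---|---|---|---|---|
| 132.5 | 3.761, 2.823 | 95.1% | 97.5% | 2.4% |
| 153.7 | 4.051, 3.040 | 97.4% | 98.8% | 1.4% |
| 159 | 4.120, 3.092 | 97.8% | 99.0% | 1.2% |

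**5. Stated FAS power, first endpoint.** Power = Φ(3.761 − z) with 132.5 events:

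| One-sided level | z | Power |
|---|---|---|
| 0.025 | 1.960 | 96.4% |
| 0.0144 | 2.186 | 94.2% |
| 0.050 | 1.645 | 98.3% |
| 0.0297 | 1.885 | 97.0% |

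The SAP's claim of at least 90% holds at every one of these levels.

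**The case against.** The best reply is that 0.025 is plainly the design level. It comes first after the success sentence, the 0.050 testing is added as a further step, results that meet only the looser rules get a lesser flag, and no power statement uses 0.050. This stands as evidence of intent, but none of it limits the success sentence.

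Second, nothing is hidden or uncontrolled. The SAP 3.3 Note prints both levels, each threshold is correct, and the tables show the flag and the "1-sided P-value for treatment comparison from Log-rank Test" (along with the two-sided one), so a reader can see which level a result met. That also stands. The flags, however, show the level that was met and not whether meeting it makes the trial positive.

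Third, the practical effect is limited. Power computed at 0.025 is conservative if 0.050 decides. No secondary test is gated on the primary result. The estimates and confidence intervals are the same either way. The option to expand was tied to blinded data and intended to sharpen the point estimate ahead of future trials. All of this is correct and keeps the point a modest one. But protocol 4.1.1 also gives the study the goal of establishing evidence of efficacy for one selected dose, so what counts as positive has consequences.

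Finally, a one-sided 0.050 level can be defended in a Phase II dose-finding trial. It can, provided it is named as the deciding level.

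**Conclusion.** The concern holds and should be fixed. The success rule names no level, two are on offer, and the rule as literally written has a one-sided type 1 error of 5.0%, where the design and power text rest on 2.5%. The Hochberg thresholds, the control of error within each procedure and the stated FAS power are all sound.

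The error figures are for the global null with the SAP's 98/76 split. The SAP recalculates its thresholds if the counts differ, so each procedure would stay at its nominal level. The success probabilities at hazard ratio 0.5 rest on the SAP's event proportions, 2:1 allocation, a mild share of 98/174, and an equal hazard ratio in mild and moderate subjects, which the SAP does not state.

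**What to change.** Before unblinding, state in SAP 5.1.1 and in the SAP 3.3 Note that the trial is positive only if rule (i) or (ii) is met, at overall one-sided 0.025. Label rules (iii)–(iv) and their flag descriptive, and change the footnotes to Tables 14.2.1.1 and 14.2.1.2 to match.

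If the sponsor prefers 0.050 as the deciding level, say so in the same places, state that the success rule has a 5% one-sided type 1 error, and bring the FAS power text in SAP 3.3 into line with that level.

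Either way the change is wording only, with no new data and no change in sample size. The first option gives up the looser route to success shown in step 4 of the working; the second means stating a less favourable error rate.

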## 5.2 Handling of Missing Data and Data Handling Rules

### 5.2.1 Missing Efficacy Endpoints

In general, missing data will not be imputed with the exception that for the missing viral load results post baseline (nasopharyngeal and saliva biospecimens) will be imputed using the multiple imputation (MI) methodology as described in Section 5.5.2.

For derivation of resolution of COVID-19 symptoms, scenarios of missing diary data (8 symptoms: cough, sore throat, nasal congestion, headache, chills and or sweats, myalgia, fatigue, nausea) in conjunction with vital signs of fever, SpO2 levels, and shortness of breath will be handled as follows:

- Scenario 1: For Day x assessment y (am or pm) with missing severity for some among the 8 symptom(s), if there is at least one symptom scored 2 (moderate) or 3 (severe), subject will be considered failure for Day x assessment y.
- Scenario 2: For Day x assessment y with missing severity for some among the 8 symptom(s), if all non-missing values are 0 or 1, any other symptoms left blank on Day x assessment y will be considered with severity of 0 (none) for the purposes of derivation of resolution of COVID-19 symptoms. Subject's success or failure for Day x assessment y will then be determined by the vital sign data on fever and/or SpO2 level/shortness of breath as follows:
  - If fever of  $\geq 100.5$  and is persistent for  $\geq 36$  hours or SpO2 levels  $< 96\%$  with shortness of breath, the subject will be considered a failure.
  - If SpO2 levels  $< 96\%$  and data is missing for shortness of breath, the subject will be considered a failure.
  - If SpO2 levels  $\geq 96\%$  and data is missing for shortness of breath, the subject will be considered a success.
  - If shortness of breath is "Yes" and SpO2 levels are missing, the subject will be considered a failure.

- If shortness of breath is “No”, and SpO2 levels are missing, the subject will be considered a success.
- If temperature data is missing, the subject will be considered a success if fever was <100.5 on the previous assessment and a failure if the previous two assessments were both ≥100.5.
- Scenario 3: For Day x (pm), if severity is missing for all 8 symptoms, the diary entries from the previous completed entry, either Day x (am) or Day x-1 (pm), will be carried forward for Day x (pm). For Day x (am), if severity is missing for all 8 symptoms, the diary entries from the previous completed entry, either Day x-1 (pm) or Day x-1 (am) will be carried forward for Day x (am). Same applied to fever and SpO2 level/shortness of breath.
- Scenario 4: For Day x assessment y where all 8 symptoms are scored 0 or 1, if fever or SpO2 level is missing, subject’s success or failure for Day x assessment y will be determined in the same way as in Scenario 2.

For derivation of the primary efficacy endpoints, subjects who were hospitalized due to COVID-19 will be designated as treatment failures, and right censored at 384 hours (16 days), i.e., censored at the end of the Visit 5 window.

For subjects who discontinued the study early for any reason other than hospitalization for COVID-19, only diary data up to subject’s discontinuation date will be used. For derivation of the primary efficacy endpoints such subjects will be considered censored at the time of their last assessment.

**Note:** Subjects discontinuing for any reason are ineligible to meet the success criteria on either primary efficacy endpoint because "success" requires the conditions to be met until the Day 14 visit.

The COVID-19 Composite Severity Score (CSS) at baseline is defined as the sum of the eight individual COVID-19 signs and symptoms severity scores divided by eight. For purposes of calculating the COVID-19 composite severity score in the secondary endpoint of worsening disease from baseline, subjects with missing diary card entries (reporting none of eight symptoms scored) will not be considered to have met the criteria for worsening of disease at that assessment timepoint. Subjects with incomplete diary card entries (reporting from 1 to 7 of the eight symptoms scored), will be handled by dividing the sum of all scores reported by the number of scores reported, and compared to the baseline CSS.

